### **12.5.2 Medication Errors**

A medication error is defined as any unintentional error in the prescribing, dispensing or administration of the study drug while the study drug is in the control of the healthcare professional or patient. The error may be related to the administration of a wrong drug, nature of the medication, route of administration, dosage or frequency of the treatment as specified in this protocol.

The following procedures should be followed:

- Medication errors with the study drugs regardless of whether it is associated with an AE (even if not fulfilling a definition of SAE) are to be promptly reported to the Sponsor.
- No antidote that can be used for the overdose of the study drugs is known. While carefully monitoring the patient, proactive treatment is provided by prophylactic and symptomatic methods to prevent or treat possible adverse reactions.

## 13. Statistical Analysis

Statistical analysis is performed following the plan described below. Details are specified in the separately prepared statistical analysis plan. The first version of the statistical analysis plan is prepared before the database lock. When the statistical analysis plan is changed, time of change, changed content and the reason are recorded.

### 13.1 Statistical Plan

#### 13.1.1 Timing of Statistical Analysis

Statistical analysis is performed after the completion of all patients' study. Before unblinding, preliminary examination (blinded review) of the measurement of efficacy and safety, distribution of endpoints, relationship among items and other aspects is performed to make decisions regarding the handling of patient data, statistical analysis methods and other points.

#### 13.1.2 Analysis Populations and Criteria for Handling Patient Data

##### 13.1.2.1 Analysis Population

The analysis populations of this study are defined as follows:

Table 13.1.2.1-1 Definitions of Analysis Populations

Analysis Set	Definition
Screened Patients	A group of all patients who gave consent
Enrolled Patients in observation period	A group of all patients enrolled in the observation period of this study
Enrolled Patients in treatment period	A group of all patients enrolled in the treatment period of this study
All Treated Patients	A group of patients who took the study drugs at least once among those enrolled in the observation period
Full Analysis Set (FAS)	A group of patients who took the study drugs for the treatment period at least once and have at least 1 efficacy endpoint before the start of the treatment period and during the treatment period among those enrolled in the treatment period
Per Protocol Set (PPS)	A group of patients in FAS except for those who meet the following criteria (1) Shown not to meet inclusion criteria (2) Shown to meet exclusion criteria (criteria affecting efficacy evaluation) (3) Less than 80% compliance with the treatment during the treatment period (4) Less than 70% entry rate in urination record (status of urinary incontinence) at Week 8 of the treatment period (5) Use of prohibited concomitant drugs or therapies considered to influence efficacy evaluation

Handling of the patients who are in circumstances not specified in the definition of analysis populations is determined before database lock through discussion by the Sponsor, the medical experts and other personnel.

##### 13.1.2.2 Criteria for Handling of Patient Data

The criteria for handling of patient data in the study are described below.

For problematic cases the Sponsor and the Medical Experts will discuss and determine an approach prior to database lock.

- (1) Handling of missing values and abnormal values
  - Handling of missing values in efficacy endpoints is specified for each analysis.
  - Missing values in safety endpoints are not imputed. The proportion including that of subjects with adverse events is calculated using the analysis population as the denominator for the observation period and using the number of subjects who took the study drugs for the treatment period at least once among those in the analysis population as the denominator for the treatment period.
  - The analyses will include all measured data unless the laboratory tests (eg, the effect of hemolysis during blood collection, showed obvious abnormal values). If abnormal values are excluded from the analysis, they should be specified and the reasons for exclusion should be stated.
- (2) Handling of data of patients treated by study drug different from the assigned one
  - In the analysis of the subjects treated with the study drugs or PPS, the data of patients treated with the study drug of the treatment group different from the group they are allocated to are handled as the data of the treatment group for the study drug they actually received.
  - In the analysis of FAS, the data of these subjects are handled as the data in the allocated group.

### **13.1.3 Statistical Analysis Methods**

The main statistical methods to evaluate the primary and secondary objectives of this study are described below.

#### **13.1.3.1 Patient Disposition and Demographic Characteristics**

- (1) Patient disposition
  - The number of patients enrolled will be counted so that their attribution to each analysis population can be seen, and patients excluded from the analysis populations will be listed with the reasons.
- (2) Demographic characteristics of patients
  - Distribution of the main patient background, disease characteristics and other characteristics in PPS is summarized.

#### **13.1.3.2 Primary Endpoint Analysis**

The following analyses are performed regarding the rate of change in mean number of urinary incontinence per 24 hours at Week 8 of the treatment period from baseline, which is the primary endpoint.

- (1) Main analysis
  - In PPS, the difference between the TAS-303 6 mg group and the placebo group and the difference between the TAS-303 3 mg group and the placebo group are

tested by t test using the two-sided significance level of the entire test of 5%. To consider multiplicity, the significance level for each comparison is adjusted by Hochberg's method.

(2) Sensitivity analysis of main analysis

- The evaluation in (1) is performed in FAS. Missing values are imputed using last observation carried forward (LOCF).

(3) Secondary analysis of primary endpoint

The following analyses are performed in FAS and PPS.

- Summary statistics are calculated for each treatment group. Missing values are not imputed.
- The rate of change from baseline in mean number of urinary incontinence per 24 hours for each week was analyzed using mixed-effect models for repeated measures (MMRM) to estimate the therapeutic effect of TAS-303 at Week 8 of the treatment period.
- In PPS and FAS, intergroup comparison is performed by the Wilcoxon rank sum test. Missing values are imputed by LOCF.

(4) Analysis by allocation factor

- The primary endpoint is analyzed for each condition of urinary incontinence (SUI and MUI).
- The primary endpoint is analyzed for each category of mean number of urinary incontinence per 24 hours (less than 2/day and 2 or more/day).

### 13.1.3.3 Secondary Endpoint Analysis

#### 13.1.3.3.1 Efficacy Analysis

The following analyses are performed for each treatment group in FAS and PPS.

(1) Mean number of urinary incontinence per 24 hours

- Summary statistics of measured values, rate of change from baseline and amount of change at each evaluation time point are calculated.
- The rate of change from baseline is analyzed using MMRM and the therapeutic effect of TAS-303 at all evaluation time points is estimated.
- The proportion of subjects with 50% or greater improvement in the rate of change from baseline and 95% CI at each evaluation time point are calculated.

(2) Amount of urinary incontinence by 1-hour pad test

- Summary statistics of measured values, rate of change from baseline and amount of change at each evaluation time point are calculated.
- The proportion of subjects with 2.0 g or less measured values at Week 8 of the treatment period and 95% CI are calculated.
- The proportion of subjects with 50% or greater improvement in the rate of change from baseline at Week 8 of the treatment period and 95% CI are

calculated.

- (3) Mean number of used pads per 24 hours (only in patients who used incontinence pads)
  - Summary statistics of measured values, rate of change from baseline and amount of change at each evaluation time point are calculated.
- (4) ICIQ-SF score
  - Summary statistics of total score and amount of change from baseline at each evaluation time point are calculated.
  - Summary statistics of the score for each item and amount of change from baseline at each evaluation time point are calculated.
- (5) Patient Global Impression-Improvement (PGI-I)
  - Proportion for each rating on 7-point scale at each evaluation time point is calculated.
  - Proportion of improvement (“very much better”, “much better”, “a little better”) at each evaluation time point and 95% CI are calculated.
- (6) I-QOL score
  - Summary statistics of total score and amount of change from baseline at each evaluation time point are calculated.
  - Summary statistics of the score of each area and amount of change from baseline at each evaluation time point are calculated.
- (7) Analysis by allocation factor
  - The secondary endpoints are analyzed for each condition of urinary incontinence (SUI and MUI).
  - The secondary endpoints are analyzed for each category of mean number of urinary incontinence per 24 hours (less than 2/day and 2 or more/day).
- (8) Mean number of SUI per 24 hours

Among the incidents of urinary incontinence recorded in the urination record (bladder diary), the data of the incidents excluding those that occurred because patients “could not hold it in” are used in the following analyses.

  - Summary statistics of measured values, rate of change from baseline and amount of change at each evaluation time point are calculated.
  - The rate of change from baseline is analyzed using MMRM and the therapeutic effect of TAS-303 at all evaluation time points is estimated.
  - The proportion of subjects with 50% or greater improvement in the rate of change from baseline and 95% CI at each evaluation time point are calculated.
- (9) Mean number of UUI per 24 hours

Among the incidents of urinary incontinence recorded in the urination record (bladder

diary), the data excluding those that occurred “while coughing, laughing, sneezing, movements including standing up or engaging in sports” are used in the following analyses.

- Summary statistics of measured values, rate of change from baseline and amount of change at each evaluation time point are calculated.
- The rate of change from baseline is analyzed using MMRM and the therapeutic effect of TAS-303 at all evaluation time points is estimated.
- The proportion of subjects with 50% or greater improvement in the rate of change from baseline and 95% CI at each evaluation time point are calculated.

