### **2.2 Secondary Objectives**

- (1) To examine the efficacy of TAS-303 using the changes in the variables including ICIQ-SF score or I-QOL score as indices and placebo as control, in female patients with SUI
- (2) To examine the dose response of TAS-303 in improvement of urinary incontinence in female patients with SUI in an exploratory manner
- (3) To examine the safety of TAS-303 using the status of onset of adverse events and other indices in female patients with SUI

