### 4.3 Patient Discontinuation Criteria

When patients meet the following conditions, administration of the study drugs is discontinued. Discontinuation criteria for individual patients are shown below.

- (1) When continuation of treatment is difficult because of onset of an adverse event
- (2) When the patient requested the withdrawal of consent
- (3) When a serious noncompliance with the study implementation procedures was noted
- (4) When continuation of the study became impossible due to a move, transfer to another hospital, busy schedule or other reasons of the patient
- (5) When a patient was found not to fulfill the criteria for subjects of this study (not meeting the inclusion criteria or meeting the exclusion criteria)
- (6) When the following liver damage for which a causal relationship with the study drugs of this study cannot be denied occurred
  - 1) AST (glutamic oxaloacetic transaminase [GOT]) or ALT (glutamic pyruvic transaminase [GPT]) > 8 × ULN
  - 2) AST (GOT) or ALT (GPT) > 5 × ULN persisting for 2 weeks or longer
  - 3) AST (GOT) or ALT (GPT) > 3 × ULN with total bilirubin (T-Bil) > 2 × ULN or international normalized ratio (INR) > 1.5
  - 4) AST (GOT) or ALT (GPT) > 3 × ULN and onset of malaise, nausea, vomiting,

right upper quadrant pain/tenderness, pyrexia, rash or eosinophilia (> 5%)

- (7) When a patient became pregnant
- (8) When the effect of the study drugs was insufficient or symptoms were exacerbated and the Investigator or Sub-investigator considered that the study should be discontinued
- (9) Other cases in which the Investigator or Sub-investigator considered the discontinuation of the study necessary

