8.1.1. Mean IEF per 24 Hours

- Summary statistics will be calculated for measured values at each evaluation time point (at the time of enrollment, Weeks 4 and 8 of treatment) and percent changes (Week 4 of treatment) as well as changes (Weeks 4 and 8 of treatment) from baseline. Summary statistics of the mean frequency of SUI episode per week will also be calculated.
- For percent changes (Weeks 4 and 8 of treatment) and changes (Weeks 4 and 8 of treatment) from baseline to each time point of evaluation, student's t-test, Wilcoxon's rank sum test, and van Elteren test using allocation adjustment factors and age (< 60 years and ≥ 60 years) as strata will be conducted using the placebo group as the control. If any stratum includes a group with 0 patient, the test will be conducted by excluding age from the strata. The van Elteren test will be performed in two patterns, i.e., a pattern in which allocation adjustment factors at the time of enrollment are used as strata (analysis in the FAS only) and a pattern in which allocation adjustment factors recorded in CRF are used as strata.
- For percent change and changes from baseline at each week, MMRM will be performed using treatment groups, evaluation time points (Weeks 4 and 8 of treatment), and interactions between the treatment group and the evaluation time point as fixed effects, and allocation factors (status of urinary incontinence [SUI or MUI], mean IEF per 24 hours [≥ 2 per day or < 2 per day]) and age (≥ 60 years or < 60 years) as covariates. Thus, the least mean square (LS Mean) in each treatment

group and the difference in the LS Mean between each dose group and the placebo group and the two-sided 95% CI will be estimated at overall evaluation time points. Unstructured covariance structure will be assumed, and toeplitz type will be used in case of no convergence. If convergence is still not achieved, the First-order autoregressive \rightarrow Compound symmetry \rightarrow Variance component will be used in this order. The Kenward-Roger method $(2009)^{4}$ will be used to calculate degrees of freedom.

• The percentage of patients with at least 50% reduction from baseline at each time point (Weeks 4 and 8 of treatment) and its 95% confidence interval (CI) will be calculated, and Fisher's exact test with placebo as the control will be conducted.

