8.1.4. ICIQ-SF score

- Summary statistics for the total score (at the time of enrollment in the observation period, at the time of enrollment in the treatment period, and Weeks 4 and 8 of treatment) and change (Weeks 4 and 8 of treatment) from baseline at each time point will be calculated.
- Summary statistics for the subscale score (at the time of enrollment in the observation period, at the time of enrollment in the treatment period, and Weeks 4 and 8 of

treatment) and change (Weeks 4 and 8 of treatment) from baseline at each time point will be calculated.

- For the change in the total score from baseline to each evaluation time point (Weeks 4 and 8 of treatment), student's t-test will be conducted using the placebo group as the control.
- For the change in the subscale score from baseline to each evaluation time point (Weeks 4 and 8 of treatment), student's t-test will be conducted using the placebo group as the control.

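### ICIQ-SF and I-QOL get only per-visit t-tests with no missing-data rule, so read as written the FAS Week 8 comparison drops patients without a Week 8 score; adding the existing MMRM is a cheap, modest improvement

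*Protocol*

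**What the plan says.** - **Objective.** Protocol 2.2, secondary objective (1), examines efficacy "using the changes in the variables including ICIQ-SF score or I-QOL score as indices and placebo as control".
- **Protocol analysis.** Section 13.1.3.3.1, items (4) and (6), in FAS and PPS: "Summary statistics of total score and amount of change from baseline at each evaluation time point are calculated". No test, model or missing-data rule is given for either score.
- **SAP analysis.** Section 8.1.4 adds, for the "change in the total score from baseline to each evaluation time point (Weeks 4 and 8 of treatment), student's t-test will be conducted", with placebo as control. Section 8.1.6 does the same for I-QOL. Subscale and domain scores are treated alike.
- **Missing data.** Protocol 13.1.2.2: "Handling of missing values in efficacy endpoints is specified for each analysis". SAP 11.2 repeats this. SAP 8.1.4 and 8.1.6 then specify nothing.
- **Comparator in the same plan.** SAP 8.1.1, on incontinence episode frequency: "For percent change and changes from baseline at each week, MMRM will be performed using treatment groups", visits and their interaction. SAP 8.1.7 and 8.1.8 do the same for SUI and UUI episodes. The primary endpoint has LOCF in the FAS (SAP 7.2).
- **Analysis sets.** The FAS needs one efficacy value before and one during treatment, not a Week 8 value (SAP 3.2).
- **Timing.** Both scores are collected at treatment-period enrollment, Week 4 and Week 8 (Protocol 2.3.2.1). Protocol Table 5-2 also schedules them at discontinuation, as far as possible.

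**The concern.** A t-test on Week 8 change, with nothing imputed, can use only patients who have a Week 8 change. Someone who attends Week 4 and then leaves is in the FAS, but her Week 4 score plays no part in the Week 8 result. Such patients need not be a random subset: Protocol 4.3 lists among the reasons to stop "When the effect of the study drugs was insufficient or symptoms were exacerbated", and also adverse events. If these reasons act at different rates in the arms, the comparison of those remaining is biased, and the direction depends on which arm loses more poor responders. The plan already has a method that uses the Week 4 value. It applies that method to episode frequency, including SUI and UUI frequency, which are not in the endpoint list of Protocol 2.3.2.1, but not to two scores that the objective names.

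**Working it through.** **1. The plan's own figure.** The documents give no sizing for these scores. The primary-endpoint sizing (SAP 2.2.2) supplies the number per group and the withdrawal rate.
- Inputs: difference 20, SD 35, two-sided 2.5% per comparison, power 90%, withdrawal about 5%.
- n = 2(2.2414 + 1.2816)² × (35/20)² = 76.02, so 77 per group; 77/0.95 gives 82, or 246 in total.
- The t-based version gives 78; 78/0.95 gives 83, or 249 in total.
- The stated 83 per group and approximately 250 are reproduced.
- At 5% withdrawal about 83 × 0.95 = 79 per group have a Week 8 score; about 4 do not.

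**2. Precision.** Suppose everyone is seen at Week 4, a share d is missing at Week 8, and the Week 4 to Week 8 correlation is ρ. The variance ratio of MMRM to observed-case is then (1 − d)ρ² + (1 − ρ²).
- d = 0.05: 0.996 at ρ = 0.3 and 0.976 at ρ = 0.7, a gain of about 0.5% to 2.5%.
- d = 0.15: 0.99 and 0.93.

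Precision is therefore not the issue.

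**3. Bias by formula.** Let leavers be k SD worse than stayers at Week 4, with dropout depending only on that score. The stayers' Week 8 mean is off by d × ρ × k in each arm, so the difference is off by (d₁ − d₂) × ρ × k. With ρ = 0.7 and k = 1:
- 7% against 3%: 0.04 × 0.7 = 0.028 SD.
- 10% against 5%: 0.05 × 0.7 = 0.035 SD.
- 15% against 5%: 0.10 × 0.7 = 0.07 SD.

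**4. Bias by simulation.** Assumed: 83 per arm, ρ = 0.7, true differences 0.30 SD at Week 4 and 0.40 SD at Week 8, and dropout after Week 4 weighted by exp(Week 4 change), so that poor responders leave more.

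| Dropout, placebo / active | Week 8 scores only (SE) | Likelihood-based, as in an MMRM (SE) |
|---|---|---|
| 5% / 5% | 0.40 | 0.40 |
| 6% / 4% | 0.388 | about 0.40 |
| 7% / 3% | 0.375 | about 0.40 |
| 10% / 5% | 0.367 (0.162) | 0.399 (0.159) |
| 15% / 5% | 0.331 (0.164) | 0.397 (0.160) |
| 5% / 15% | 0.468 (0.163) | 0.403 (0.160) |

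Power is Φ(difference/SE − 1.96), at two-sided 5% per comparison. It is 62% against 71% at 10%/5%, and 52% against 70% at 15%/5%.

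A second simulation assumed ρ = 0.6 and logistic dropout on the Week 4 score, with more dropout on active. The observed-case bias was about 0 at 5% in both arms, 0.04 SD at 10% against 5%, and 0.07 SD at 15% against 5%. It was also 0.07 SD at 5% in both arms if poor responders leave one arm and good responders the other.

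**5. Limit of the remedy.** Steps 2 to 4 give everyone a Week 4 score. If half of the dropouts leave before Week 4 (an assumption), the likelihood-based estimate is 0.383 at 10%/5% and 0.372 at 15%/5%, against a true 0.40. It then removes about half of the bias.

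**6. The PPS.** SAP 6.1.3.1 divides treatment days by at least 56, so a patient who stops near Week 4 has about 28/56 = 50% compliance. She fails the 80% rule, and usually the Week 8 diary rule too (SAP 3.2). An MMRM in the PPS would recover almost no one.

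**The case against.** The strongest reply is that the plan expects about 5% withdrawal, and that with similar dropout across the arms nothing is biased and almost nothing is gained. That stands, and it limits the size of the point. The 10% and 15% scenarios go beyond the planning assumption, and nothing in the documents suggests opposite reasons for leaving in the two arms.

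Three stronger readings that a reader might infer are not supported:
- *The documents prescribe a completer analysis.* They do not; it is the default reading of a t-test without a missing-data rule. Scores are also scheduled at discontinuation, and no section says whether they count as Week 8. SAP 12 places the full list of analyses in a Table and Figure Plan that is not part of these documents.
- *Secondary objective (1) stands or falls on these scores.* Its wording covers other variables too, and Protocol 2.3.2.1 lists the pad test, pad use, PGI-I and episode frequency. The scores have no success criterion and lie outside the Hochberg adjustment (SAP 11.5).
- *The FAS result merely repeats the PPS result.* The FAS also keeps ineligible patients, poor compliers and users of prohibited treatments who do have Week 8 scores.

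What remains is that both documents promise a rule per analysis and none is given for these two scores.

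**Conclusion.** The gap is real and the consequence modest. At the planned average withdrawal of about 5%, the likely bias is 0 to 0.03 SD if reasons for leaving are alike in the arms. At 10% to 15% in one arm and 5% in the other, it is about 0.03 to 0.07 SD. The standard error is about 0.16 SD, so even the upper figure is less than half of it (0.07/0.16 = 0.44). The direction cannot be told in advance. These sizes rest on assumed correlations of 0.6 to 0.7 and on assumed dropout patterns. The documents give no SD or visit correlation for either score, and no dropout by arm. The size also depends on discontinuation scores not being counted as Week 8. This is a worthwhile improvement to a secondary analysis, not a threat to the primary result.

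**What to change.** - In SAP 8.1.4 and 8.1.6, add for the FAS the SAP 8.1.1 MMRM on change in ICIQ-SF total and I-QOL total. Use treatment, visit and their interaction, the same covariates, unstructured covariance with the same fallback order, and Kenward-Roger degrees of freedom.
- Report the Week 8 difference of each dose from placebo with its 95% CI. Neither section now asks for a between-group estimate with an interval.
- Keep the t-tests, labelled as observed-case support.
- State the visit to which scores taken at discontinuation are assigned. Without this the MMRM leaves part of the gap open.
- An MMRM in the PPS is optional.

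**Cost.** A few lines of SAP text and a rerun of specified model code on two more variables; no new data. The model relies on missing-at-random, as the existing MMRM does, and gives no help for patients without a Week 4 score. SAP version 2.0 was revised before key code breaking and version 3.0 added further analyses; the documents do not say whether the codes had been broken by then. If the MMRM is added after that point, SAP 10 requires it to be logged and kept apart from the pre-planned analyses, that is, as post hoc.
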